7.8 Patient Treatment Discontinuation

In the event of discontinuation of study treatment, e.g. completing treatment, unacceptable toxicity or patient choice, full details of the reason/s for discontinuation should be recorded on the appropriate pages on the CRF. All patients, including non-compliant patients, should be followed up according to the protocol unless they withdraw specific consent. Patients who stop treatment due to adverse experiences (clinical or laboratory) will be treated and followed according to accepted medical practice. All pertinent information concerning the outcome of such treatment must be recorded in the CRF.

The following are justifiable reasons for the Investigator to stop study treatment:

- unforeseen events: any event which in the judgement of the Investigator makes further treatment inadvisable
- serious violation of the study protocol (including persistent patient non-attendance and persistent non-compliance)
- stopping by the Investigator for clinical reasons not related to the study drug treatment

Patients must stop study treatment in the event of:

- unacceptable toxicity (detailed below)
- SAE requiring permanent discontinuation of treatment
- the patient becoming pregnant
- Disease Progression

Table 5. Adverse Events requiring avelumab discontinuation or modification

Any Grade 4 AEs

 • except for single laboratory values out of normal range that are unlikely related to study treatment as assessed by the Investigator, do not have any clinical correlate, and resolve within 7 days with adequate medical management
Any Grade 3 AEs except for any of the following:

 • Transient (\leq 6 hours) Grade 3 flu-like symptoms or fever, which is controlled with medical management • Transient (\leq 24 hours) Grade 3 fatigue, local reactions, headache, nausea, emesis that resolves to Grade \leq 1 • Single laboratory values out of normal range that are unlikely related to study treatment according to the Investigator, do not have any clinical correlate, and resolve to Grade \leq 1 within 7 days with adequate medical management • Tumor flare phenomenon defined as local pain, irritation, or rash localized at sites of known or suspected tumor • Change in ECOG PS to \geq 3 that does not resolve to \leq 2 within 14 days (infusions should not be given on the following cycle, if the ECOG PS is \geq 3 on the day of study drug administration) • First occurrence of a Grade 3 IRR that meets conditions for continued therapy as outlined in Table 3.
Any Grade 2 AE should be managed as follows:

 • If a Grade 2 AE resolves to Grade \leq 1 by the last day of the current cycle, treatment may continue. • If a Grade 2 AE does not resolve to Grade \leq 1 by the last day of the current cycle, infusions should not be given on the following cycle. If at the end of the following cycle the event has not resolved to Grade 1, the patient should permanently discontinue treatment with a avelumab AE (except for hormone insufficiencies, that can be managed by replacement therapy; for these hormone insufficiencies, up to 2 subsequent doses may be omitted). • Upon the second occurrence of the same Grade 2 AE (except for IRR or hormone

insufficiencies that can be managed by replacement therapy) in the same patient, treatment with avelumab has to be permanently discontinued.

- Recurrent Grade 2 IRRs may not require treatment discontinuation and should be managed as outlined in Table 3

When a patient stops trial treatment an End of Treatment visit should be performed 28 days (+/- 5 days) after their last dose of avelumab. Assessments are to be performed as per section 7.3 and include:

- Physical Exam
- ECOG
- Vital signs
- Full blood count
- Biochemistry
- Hormone function
- Pregnancy test
- Urinalysis
- 12- lead ECG
- Disease assessment
- Adverse events

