7.3.3 Electrocardiogram (ECG)

Single 12 lead ECGs will be performed at baseline, on Day 1 of Cycles 1 and 2, before avelumab infusion, and at the end of avelumab infusion. This will also be repeated at the End of Treatment visit.

If the QTc is prolonged (>500 msec, ie, CTCAE Grade 3), then the ECGs should be re-evaluated by a qualified person at the site for confirmation as soon as the finding is made, including verification that the machine reading is accurate. If manual reading verifies a QTc of >500 msec, immediate correction for reversible causes (including electrolyte abnormalities, hypoxia and concomitant medications for drugs with the potential to prolong the QTc interval) should be performed. In addition, repeat ECGs should be immediately performed hourly for at least 3 hours until the QTc interval falls below 500 msec. If QTc interval reverts to less than 500 msec, and in the judgment of the investigator(s) and Sponsor is determined to be due to cause(s) other than investigational product, treatment may be continued with regular ECG monitoring. If in that timeframe the QTc intervals rise above 500 msec the investigational product will be held until the QTc interval decreases to 500 msec. If the QTc interval has still not decreased to 500 msec after 2 weeks, or if at any time a patient has a QTc interval >515 msec or becomes symptomatic, the patient will be removed from the study.

An electronic reading of prolonged QTc must be confirmed by manual reading. Prior to concluding that an episode of prolongation of the QTc interval is due to investigational product, thorough consideration should be given to potential precipitating factors (eg, change in patient clinical condition, effect of concurrent medication, electrolyte disturbance) and possible evaluation by specialist.

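### Table 5 lists an unresolved fall to ECOG PS 3 or worse as an exception to the Grade 3 rule: the wording is inverted or misplaced, and the resulting hold has no stated end (low severity)

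*Combined protocol and SAP*

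**What the plan says.** Section 7.8 makes unacceptable toxicity a mandatory reason to stop and defines it through Table 5. The Grade 3 row of that table opens "Any Grade 3 AEs except for any of the following". Among the bullets under it is a change in ECOG PS to 3 or worse "that does not resolve to" 2 or better within 14 days. A parenthesis adds the only action: "infusions should not be given on the following cycle, if the ECOG PS is" 3 or worse on the day avelumab is due.

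The neighbouring exceptions are worded the other way. They cover transient "Grade 3 flu-like symptoms or fever, which is controlled with medical management" (limit 6 hours) and Grade 3 "fatigue, local reactions, headache, nausea, emesis that resolves to Grade" 1 or lower (limit 24 hours). The Grade 4 row exempts isolated laboratory values that "do not have any clinical correlate, and resolve within 7 days with adequate medical management", and the Grade 3 row has a matching laboratory exception.

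Two other rules in the protocol set an end to a hold. For Grade 2 events, Table 5 says "If at the end of the following cycle the event has not resolved to Grade 1, the patient should permanently discontinue treatment", with hormone insufficiencies excepted. Section 7.3.3 removes a patient from the study "If the QTc interval has still not decreased to 500 msec after 2 weeks". Table 4 also ends treatment for a Grade 2 or 3 immune-related event that lasts 12 weeks.

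**The concern.** An exception list should spare events mild or short enough for treatment to go on. Here it spares the decline that fails to recover, while a decline that recovers in time is not on the list. Table 5 defines the mandatory stop for toxicity, so a reversed or misplaced line in it leaves sites to guess.

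At stake is consistent handling of a patient whose PS stays at 3 or worse. One site may discontinue avelumab and another may keep the patient on hold. The label has consequences: Section 7.7 bars other anti-cancer treatment during the treatment phase but not in post-treatment follow-up.

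**Working it through.** The plan states no figure on this point, so the check compares the text, with a little arithmetic on time limits.

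**1. Position of the bullet.** It stands between tumour flare and a first Grade 3 infusion reaction that meets the conditions for continuing. Both are true exceptions, so on the page the ECOG bullet is inside the list.

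**2. Direction of the time-limited exceptions in the Grade 3 and Grade 4 rows.**

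| Exception | Limit | What is exempt |
|---|---|---|
| Grade 4 laboratory values | 7 days | resolves |
| Grade 3 flu-like symptoms or fever | 6 hours | transient |
| Grade 3 fatigue, headache, nausea and similar | 24 hours | transient and resolves |
| Grade 3 laboratory values | 7 days | resolves |
| ECOG PS 3 or worse | 14 days | does **not** resolve |

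Four of the five exempt a transient or resolving event. Only the ECOG bullet exempts a persisting one.

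**3. Possible readings.**
- (a) A PS fall counts as a Grade 3 event and the text is literal: the lasting decline is exempt.
- (b) A PS fall is not itself a graded event: the exception removes nothing, and only the hold operates.
- (c) The bullet is a stopping criterion that landed in the wrong list: a stop at 14 days is intended.

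Under (a) and (b) the PS decline has no stated stop; under (c) it has one. The documents do not say which was meant.

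**4. Search for another PS rule.** The pre-dose criteria in Section 7.2 cover platelets, neutrophils, bilirubin, creatinine clearance and transaminases, not PS. The mandatory stops in Section 7.8 are toxicity (through Table 5), certain SAEs, pregnancy and progression; none names PS. Section 4.1 uses PS for entry. Section 7.3.5 mentions it only as part of judging early scans. No other section gives a mandatory stop tied to PS.

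**5. Time to a mandatory end under other rules.**
- QTc: 2 weeks = 2 × 7 = 14 days.
- Grade 2 event starting on day d of a 28-day cycle and unresolved at the end of the following cycle: (28 − d) + 28 = 56 − d days. That is 55 days for d = 1 and 28 days for d = 28.
- Immune-related Grade 2 or 3 event: 12 × 7 = 84 days.
- PS hold: no end stated.

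**6. ECOG readings.** Section 7.3.4 and Table 2 schedule ECOG on day 1 of each cycle and at the End of Treatment visit. A decline found on day 1 reaches its 14-day limit on day 1 + 14 = day 15. That is a dosing visit, but no ECOG is scheduled; the next routine reading is day 1 of the next cycle.

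**The case against.** The strongest reply is that this is a drafting slip with almost no patient left in the gap. Reading (c) is natural: the table's title covers both discontinuation and modification, and the bullet's wording would serve as a stopping criterion. The infusion-reaction bullet after it does not rule this out; the amendment log records that Table 5 was later aligned with Table 3, so that bullet may have been added afterwards (an inference). Grade 3 fatigue that outlasts 24 hours falls under the Grade 3 rule. Persistent Grade 2 events, Grade 4 events and progression have rules of their own. Section 7.8 also lets the investigator stop for clinical reasons unconnected with avelumab. Most of this stands, and it is why severity is low.

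The reply is also right that the comparators in step 5 are toxicity rules, whereas a PS decline may come from the lymphoma. They show that the protocol normally gives its holds an end; they do not establish that the end should be 14 days. An unconditional permanent stop at 14 days would also clash with Table 4. A first Grade 3 colitis, for example, is held, treated with steroids tapered over at least 1 month, and then allowed back on avelumab.

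A reader might infer that the End of Treatment visit or safety follow-up is lost during an open-ended hold. The text does not support that: both are timed from the last dose (28 and 30 days), and scans and examinations run by cycle. The point that survives is narrower: no reading of the current page tells a site, without guessing, when the PS hold ends.

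**Conclusion.** The bullet is wrong as written, at low severity. Either its direction is inverted or it is a stopping criterion in the wrong list. The remaining effect is that the PS hold has no stated end, so sites may classify the same patient differently.

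Two stronger conclusions are tempting and should not be drawn. One is that patients with a lasting PS of 3 or worse would go on being dosed: the parenthesis blocks an infusion while PS is 3 or worse on the dosing day. The other is that the trial's result is at risk: Section 12.2 counts responders over all registered patients and classes those who cannot be assessed as non-responders, so the primary analysis does not depend on this line. Nor can it be said that no stop was intended, given reading (c).

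The documents give no frequency for such declines, so the number of patients affected cannot be estimated. The verdict rests on the printed structure of Table 5 and on the absence of a PS-based stop elsewhere.

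**What to change.** Subject to the sponsor confirming what was intended:

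1. Take the ECOG bullet out of the Grade 3 exceptions. If an exception is wanted, word it as a decline that recovers to PS 2 or better within 14 days. That change alone would not be enough, because it creates a stop only if a PS decline counts as a Grade 3 event.
2. State separately in Table 5 that avelumab is discontinued when PS of 3 or worse has not recovered to 2 or better within 14 days. Except declines due to an immune-related event being managed under Table 4; for these, Table 4's rules on holding, resuming and the 12-week limit apply.
3. Keep the dosing-day hold. In patients whose PS has fallen to 3 or worse, record ECOG before any dose, including day 15.

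The cost is one line moved and restated, a cross-reference to Table 4, a few extra ECOG checks and an occasional earlier stop. Endpoints, sample size and analysis do not change.

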7.2 Treatment Schedule

Avelumab 10 mg/kg will be administered once every 14 days for a proposed duration of 8 cycles (28 day cycles), (16 doses).

If the patient is showing clinical benefit following 8 cycles of trial treatment patients may continue to receive avelumab treatment at the treating Investigator's discretion, until loss of response, toxicity, or death.

Every effort should be made for patients to attend on the scheduled visit days. However, if a patient is unable to attend on the specified day, assessments may be scheduled for +/- 3 days.

The full blood count should be assessed prior to each treatment (within 24 hours of treatment) to ensure the following criteria are met:

- Platelets $> 75 \times 10^9/L$
- Neutrophils $> 1.0 \times 10^9/L$
- Bilirubin $< 1.5 \times ULN$
- Creatinine clearance (CrCL) (Cockcroft-Gault) $\geq 30 \text{ ml/min}$.
- ALT/AST $\leq 1.5 \times ULN$ on Cycle 1 day1; thereafter $\leq 3 \times ULN$

Please also refer to Section 7.5 for dose delays and modifications, and to section 7.7 for concomitant medications.

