7.5.4 Management of Immune-Related Adverse Events

Since inhibition of PD-L1 stimulates the immune system, immune-related Adverse Events (AEs) may occur. Avelumab can result in severe and fatal immune-related adverse reactions. These immune-related reactions may involve any organ system. Most immune-related reactions initially manifest during avelumab treatment; however, immune-related adverse reactions can occur after discontinuation of avelumab.

Monitor patients for signs and symptoms of pneumonitis, colitis, changes in thyroid function, adrenal insufficiency, hyperglycaemia (or other signs and symptoms of diabetes), abnormal liver tests and elevated serum creatinine at the start of treatment and periodically during treatment.

Treatment of AEs is mainly dependent upon severity (NCI-CTCAE grade):

Grade 1 to 2: treat symptomatically or with moderate dose steroids, more frequent monitoring

Grade 1 to 2 (persistent): manage similar to high grade AE (Grade 3 to 4)

Grade 3 to 4: treat with high dose corticosteroids

Treatment of gastrointestinal, dermatological, pulmonary, hepatic, renal, endocrine and Cardiac AEs should follow guidelines set forth in the table below Table 4.

Table 4. Management of Immune-Related Adverse Events

Gastrointestinal AEs		
Severity of Diarrhea / Colitis (NCI-CTCAE v4.03)	Management	Follow-up
Grade 1 Diarrhea: < 4 stools/day over Baseline Colitis: asymptomatic	Continue avelumab therapy Symptomatic treatment (for example, loperamide)	Close monitoring for worsening symptoms Educate subject to report worsening immediately If worsens: Treat as Grade 2 or 3/4
Grade 2 Diarrhea: 4 to 6 stools per day over Baseline; IV fluids indicated < 24 hours; not interfering with ADL Colitis: abdominal pain; blood in stool	Withhold avelumab therapy Symptomatic treatment Treat Grade 2 colitis with 1.0 to 2.0 mg/kg/day prednisolone IV or equivalent	If improves to Grade 1: Resume avelumab therapy For Grade 2 colitis continue steroids until Grade 1, then taper over at least 1 month; resume Avelumab therapy following steroids taper. If persists > 5 to 7 days or recur: Treat as Grade 3 to 4

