Grade 3 to 4 Diarrhea (Grade 3): ≥ 7 stools per day over Baseline; incontinence; IV fluids ≥ 24 hrs.; interfering with ADL Colitis (Grade 3): severe abdominal pain, medical intervention indicated, peritoneal signs Grade 4: life-threatening, perforation	Withhold avelumab for Grade 3. 1.0 to 2.0 mg/kg/day prednisolone IV or equivalent Add prophylactic antibiotics for opportunistic infections Consider lower GI endoscopy. Permanently discontinue avelumab for Grade 4 or recurrent Grade 3.	If improves: Continue steroids until Grade 1, then taper over at least 1 month; resume Avelumab therapy following steroids taper (for initial Grade 3). If worsens, persists > 3 to 5 days, or recurs after improvement: Add infliximab 5 mg/kg (if no contraindication), Note: Infliximab should not be used in cases of perforation or sepsis
Dermatological AEs		
Grade of Rash (NCI-CTCAE v4.03)	Management	Follow-up
Grade 1 to 2 Covering ≤ 30% body surface area	Symptomatic therapy (for example, antihistamines, topical steroids) Continue avelumab therapy	If persists > 1 to 2 weeks or recurs: Withhold Avelumab therapy Consider skin biopsy Consider 0.5 to 1.0 mg/kg/day prednisolone or equivalent. Once improving, taper steroids over at least 1 month, consider prophylactic antibiotics for opportunistic infections, and resume avelumab therapy following steroids taper. If worsens: Treat as Grade 3 to 4

Grade 3 to 4 Grade 3: Covering > 30% body surface area; Grade 4: life threatening consequences	Withhold avelumab for Grade 3. Permanently discontinue avelumab for Grade 4 or recurrent Grade 3. Consider skin biopsy Dermatology consult 1.0 to 2.0 mg/kg/day prednisolone or equivalent Add prophylactic antibiotics for opportunistic infections	If improves to Grade ≤1: Taper steroids over at least 1 month; resume Avelumab therapy following steroids taper (for initial Grade 3).
Pulmonary AEs		
Grade of Pneumonitis (NCI-CTCAE v4.03)	Management	Follow-up
Grade 1 Radiographic changes only	Consider withholding avelumab therapy Monitor for symptoms every 2 to 3 days Consider Pulmonary and Infectious Disease consults	Re-assess at least every 3 weeks If worsens: Treat as Grade 2 or Grade 3 to 4

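### For a second Grade 2 immune-related rash, Table 4 says resume avelumab and Table 5 says stop permanently, and nothing says which table prevails

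*Combined protocol and SAP*

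**What the plan says.** Two tables in the protocol govern avelumab after a recurrent Grade 2 event.

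- **Table 4 (section 7.5.4, dermatological AEs).** Grade 1 and Grade 2 rash share one row. Its follow-up column begins "If persists > 1 to 2 weeks or recurs: Withhold Avelumab therapy". It then offers steroids as an option ("Consider 0.5 to 1.0 mg/kg/day prednisolone or equivalent"), to be tapered over at least a month once the rash is improving, and ends "consider prophylactic antibiotics for opportunistic infections, and resume avelumab therapy following steroids taper".
- **Table 5 (section 7.8).** The block covering every Grade 2 AE says "Upon the second occurrence of the same Grade 2 AE (except for IRR or hormone" insufficiencies that replacement therapy can manage) "in the same patient, treatment with avelumab has to be permanently discontinued".

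Three other sentences direct sites to one table or the other:

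- Section 7.2: "Please also refer to Section 7.5 for dose delays and modifications".
- Section 7.5.4: "Treatment of gastrointestinal, dermatological, pulmonary, hepatic, renal, endocrine and Cardiac AEs should follow guidelines set forth in the table below Table 4".
- Section 7.8, which leads to Table 5 through its entry for unacceptable toxicity: "Patients must stop study treatment in the event of".

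Table 5 hands recurrent Grade 2 infusion reactions to Table 3. It has no similar pointer to Table 4, and Table 4 does not mention Table 5.

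**The concern.** A patient whose Grade 2 rash clears and then returns at Grade 2 meets both rules. One ends trial treatment and the other restarts it. The Synopsis plans 13 centres, so the same event could be handled differently from centre to centre, with each investigator able to point to protocol text in support.

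For that patient the difference is between losing treatment for an aggressive lymphoma and being re-exposed to a drug whose immune-related reactions, as section 7.5.4 warns, can be severe or fatal. For the trial, whichever choice is made can be recorded as a departure from one of the two tables.

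**Working it through.** No arithmetic decides the main point. The check is to trace one patient through both tables and then look for a rule that ranks them.

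**Case: second Grade 2 rash covering no more than 30% of body surface, with the earlier Grade 2 rash resolved.**

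| Step | Table 4, section 7.5.4 | Table 5, section 7.8 |
|---|---|---|
| Does the row apply? | Yes: the row covers Grade 1 and Grade 2, and recurrence is a named trigger | Yes: the block covers all Grade 2 AEs, and this is the same AE a second time |
| Is the event exempt? | No exemption stated | No: only infusion reactions and replaceable hormone insufficiencies are exempt |
| Immediate action | Withhold | Discontinue |
| End state | Resume after taper | Permanent stop |

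Both tables interrupt avelumab, so the conflict lies in the end state.

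**Is there a precedence rule?**

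1. Section 7.2 sends the reader to section 7.5 for delays and modifications and does not mention section 7.8.
2. Section 7.5.4 says how organ-specific AEs are to be treated, names dermatological events and points to Table 4. It does not say that Table 4 displaces the stopping rules in section 7.8.
3. Section 7.8 is worded as mandatory, but does not say that it overrides Table 4.
4. The general line in section 7.5.4 that persistent Grade 1 to 2 events are managed like high-grade ones does not settle it. Table 4 allows resumption after an initial Grade 3 rash as well.

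None of these ranks the tables.

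**Does the conflict extend to other events?**

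- *Other immune-related AEs.* Table 4 withholds and resumes at Grade 2 and states a recurrence stop only for Grade 3. It has no rule for a second Grade 2 event, so Table 5 can fill the gap. This is silence, not contradiction.
- *Persistence of such events.* Table 5 stops at the end of the cycle after the one in which the event began: 0 to 28 days left in the current cycle + 28 days = 28 to 56 days from onset. Table 4 stops at 12 weeks = 12 × 7 = 84 days, or sooner in effect through its separate stop for 10 mg/day or more of prednisone beyond 12 weeks, if steroids began before the event reached that limit. The limits differ, but applying the earlier one satisfies both.
- *Hepatic events.* Table 4 is the stricter: Grade 2 elevations lasting more than 5 to 7 days move to the permanent-stop row.
- *Colitis.* Table 4 escalates recurrent Grade 2 to its Grade 3 to 4 row. That row resumes after an initial Grade 3 and stops after a recurrent one, and the text does not say how an escalated Grade 2 counts. This is unclear, but not a direct contradiction.

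The firm conflict is therefore recurrent Grade 2 rash alone.

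**The case against.** The best defence is that the two texts differ in force. Table 4 is introduced as guidance that should be followed, and parts of the rash row are only things to consider. Section 7.8 says patients must stop, and Table 5 says avelumab has to be discontinued. On the usual reading a mandatory stop limits management guidance, and a listed set of exceptions that omits rash is meant to omit it. A harmonising reading is also available: if Table 5 takes the second Grade 2 rash, the word for recurrence in Table 4 still covers recurrent Grade 1, or Grade 2 following Grade 1.

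Much of this stands. A cautious site that stops has a defensible position, and this is the reason to make Table 5 the default in the fix. It does not remove the conflict. The rash row carries no such limit on grade, its instruction to resume is not optional in wording, and a site that resumes is also following protocol text.

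A reader might make the opposite inference, that section 7.5.4 makes Table 4 prevail for dermatological events. The documents do not support that either: the sentence directs treatment of the AE and leaves the stopping rules of section 7.8 untouched.

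**Conclusion.** The inconsistency is real and confined to a second Grade 2 immune-related rash: permanent stop under Table 5, withhold and resume under Table 4, with no stated precedence. It should be fixed because it concerns safety and uniform dosing and costs almost nothing to remove.

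Three larger claims might be inferred, and the documents do not support them.

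- *A general clash between the tables at Grade 2.* For other immune-related AEs and for persistence limits, a site can comply by following Table 5 or the earlier limit.
- *A patient count.* Section 1.2.3 gives 56/480 = 11.7% with potential autoimmune events, which would be 30 × 0.117 = 3.5 to 35 × 0.117 = 4.1 patients here. That figure covers potential autoimmune events of every kind. It is not broken down by rash, grade or recurrence, so it does not measure this event. Few patients are likely to be affected, but that is a judgement, not an estimate.
- *An effect on the primary result.* Section 12.2 counts responders over all registered patients, and its per-protocol set needs eligibility and one dose. Stopping or resuming after a second rash changes neither set, and no effect on the response rate can be shown.

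**What to change.** 1. Amend the Grade 1 to 2 rash row of Table 4 so that resumption after recurrence applies only to recurrent Grade 1 rash or to a first Grade 2 rash. A second Grade 2 rash stops avelumab permanently.
2. Add one sentence to Table 5: *Where Tables 4 and 5 differ for an immune-related AE, the stricter rule (earlier or permanent stop) applies.* It is best placed in the Grade 2 block. There it would not be read as turning Table 4's hold-and-resume rule for an initial Grade 3 rash or colitis into a permanent stop.

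The sentence also settles a second Grade 2 event among the other immune-related AEs, recurrent Grade 2 colitis and the differing persistence limits, and it keeps Table 4's stricter hepatic rule.

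The cost is a short protocol amendment, with no change to sample size or analysis. Amendment 4 made a similar correction when it aligned Table 5 with Table 3. The clinical downside is that a few patients with recurrent Grade 2 rash lose the option to resume. If the sponsor's clinicians want to keep that option, the alternative is to name rash among the exceptions in Table 5 and refer to Table 4, as Table 5 already does for infusion reactions and Table 3.
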